4.3 Informed Consent Procedures

One of the Investigators or a trained, research-credentialed member of the study staff will go through the informed consent process prior to the baseline evaluations for each patient who elects to participate. In order to ensure consistent and thorough administration of the ICF process for this study, study research staff will be trained by the study investigators on the ICF process and will conduct mock ICF sessions with investigators prior to performing the ICF process with participants. The ICF process will take place on a private remote videoconference (e.g., Cisco Webex, Microsoft Teams).

At the scheduled ICF and initial baseline assessment, a study staff member will confirm inclusion and exclusion criteria reported at the initial phone screening call and verbally review each section of the ICF and HIPAA forms with the Veteran. They will explain alternatives to participating in the study, such as treatment available at VA Boston Healthcare System. The study staff member will answer any questions about the study the participant might have. Participants will be given as long as they like to consider participation. If they report that they understand the study procedures and are willing to participate in the study, staff will ask participants to sign the ICF and HIPAA forms electronically using the DocuSign program. This method of informed consent and documentation has been approved for other studies by the VA Boston IRB. If DocuSign is unavailable or the participant does not want to sign the form electronically, study staff will send two hard copies of the ICF to the participant in advance of this meeting. Participants will sign the hard copies and will then be asked to hold the signed signature pages of the ICF and HIPAA forms up to the screen so study staff can capture screen shots of the signed forms to save in secure files. Given the variability in screen-shot quality, study staff will also instruct the veterans to send signed copies of the ICF and HIPAA back to [name] for VA Boston study records and to keep a signed copy of the forms for their own records.

After the informed consent document is signed, additional screening procedures covered in the informed consent document will be conducted prior to randomization. The investigators consider this consent process to be an ongoing process maintained throughout the study to provide participants with a continued understanding of the protocol, their participation, and their rights as human research subjects.

All discussions concerning consent will emphasize that participation is voluntary and that the participant's medical care/benefits will be unaffected by his or her decision regarding participation. Participants will be informed that they will be compensated for time and inconvenience at a rate of \$25 for each of the two baseline assessment sessions and \$65 for the post-treatment assessments. Those participants who are recruited for Phase Two will be compensated \$80 for the 3-month follow-up assessment. Participants will also receive \$5 for completing the weekly measures, \$5 for the weekly phone calls with study staff who track home practice/goals, and \$5 for each intervention group session they attend for a grand total of up to \$355 for those in Phase One and \$435 for those in Phase Two. In the event that a participant completes the baseline assessment twice (see paragraph below for scenario where this could occur), the potential total compensation for Phase Two could be \$485. This remuneration for time, inconvenience, and ongoing commitment is not so high as to coerce an individual to participate who would otherwise not participate. Compensation will be provided in one of three ways: 1) gift cards to a national chain store (e.g., Target or Walmart) which would be mailed to them, 2) electronic funds transfers to the participants' bank accounts (bank account information including bank routing number, account number, bank name, account type will need to be confirmed), or by 3) debit card payments using Direct Express (participants will need to request a debit card or provide account information if they already have one) and payments will be made directly to the debit card. If gift cards are sent to participants, a templated thank you letter with a breakdown of the gift card payments will be mailed with the gift cards to ensure participants can keep track of (for their own records) the payments they have received throughout the study and what they were for.

Some participants may complete the consenting process but not complete the entire baseline assessment in a timely manner due to illness or other unforeseen reasons. If a participant completed or partially completed a baseline assessment, but is not able to participate in the upcoming cohort, they may be considered for a later cohort. In this case, the participant will be reconsented, baseline measures will be readministered, the participant will be compensated for the additional baseline assessment, and the original baseline measures will not be included for analysis.

[Note: If there is a delay before the second baseline session and the only measure the participant is asked to re-take is the sit to stand task (see below under Study Evaluation for explanation of that), no additional compensation will be provided. This measure takes approximately 5 minutes to administer.]

There will be no circumstances under which a legal authorized representative will provide consent for a participant enrolled in the study. Participants will also be informed that if suicidal intentions, or child or elder abuse are disclosed, confidentiality may be broken for protective measures to be taken.

4.4 Inclusion/Exclusion Criteria

The primary inclusion criteria for this study will be Veterans with PTSD and chronic musculoskeletal pain who agree to abstain from initiating other formal treatments for PTSD during the study period. A more complete description of both the inclusion and exclusion criteria is located in the table below.

An initial screening will take place over the telephone (or in person if the potential participant stops by the research office) to determine if the veteran meets initial inclusion criteria. (Please see Telephone Screening Form.) Telephone screening forms for veterans, including those who do not meet all inclusion criteria, will be completed digitally and kept in a secure data folder on our shared drive (specified below). In the event that we seek and gain IRB approval to amend our inclusion criteria at a future date (e.g. loosen the criteria to include more veterans), we will submit a HIPAA waiver for IRB approval to allow us to access the forms for those who did not originally meet eligibility criteria and to re-contact those individuals who may now be eligible to participate. Additionally, participants who are deemed ineligible after screening will be asked if they would like to be added to the Subject Recruitment Database, in which case they will be mailed the relevant form at a later date.

Final eligibility for the study will be determined after the baseline assessment is completed. The informed consent process will occur prior to initiating the baseline assessment. The CAPS-5 interview to determine the PTSD case definition will take place during part two of the baseline assessment after the informed consent process in part one of the baseline assessment. If veterans do not meet the diagnostic criteria on the CAPS-5, they will be determined ineligible at this point. In addition, if information comes to light during the baseline assessment that indicates ineligibility (e.g., veteran mentions they recently began a new treatment or had a psychiatric hospitalization), they will not be added to the list of participants to be randomized. We anticipate that a small number of veterans may be screened out after the informed consent process and prior to randomization. These veterans will be compensated for participation in the baseline assessment but will be deemed ineligible for the remainder of the study and will not be randomized.

Inclusion criteria	Exclusion criteria

- Veteran status as indicated by self-report- PTSD Case Definition. Veterans who meet DSM-5 diagnostic criteria according to DSM-5 diagnostic algorithm for current PTSD as assessed on the Clinician-Administered PTSD Scale for DSM-5 (CAPS-5) will be eligible for the study. A diagnosis of current PTSD requires: a traumatic stressor (Criterion A) and the requisite number of symptoms at a severity level of 2 or higher in each symptom cluster. Each symptom is rated on a severity scale of 0 (no symptoms) to 4 (extreme), with 2 representing clinically significant and clearly present symptomatology. An individual must endorse at least one reexperiencing (Criterion B) symptom, at least one	
- Lacks the capacity to provide consent.- Diagnosed major medical disorder (e.g., neurological disorder, cancer, chronic infectious disease or liver disease) or has a moderate or severe traumatic brain injury, which could otherwise explain the health symptoms or interfere with their ability to safely engage in Tai Chi exercises.- Change in psychotropic or pain medication during the past month. This will minimize amount of symptom change due to medication alterations. (Once enrolled, medication changes are nonetheless expected and will be monitored.)- Regular current Tai Chi, formal mindfulness meditation program, or yoga practice, defined as at least three hours per week for more than three months. (Veterans with


avoidance (Criterion C) symptom, at least two symptoms of negative alterations in cognition and mood (Criterion D), and at least two hyperarousal (Criterion E) symptoms. In addition, these symptoms must have been present for at least one month (Criterion F) and cause either clinically significant distress or functional impairment (Criterion G).
 
 - Chronic pain as indicated by complaints of musculoskeletal pain in one or more body regions for six months or more. - Willing to abstain from initiating evidence-based and mindfulness-based psychotherapy for PTSD, pain and related disorders until completion of the study (i.e., prolonged exposure, cognitive processing therapy, cognitive-behavioral treatment for insomnia or pain, acceptance and commitment therapy, dialectical behavior therapy, mindfulness-based stress reduction). Once enrolled, however, if other providers prescribe treatment or if participants require additional intervention (such as to manage a safety or substance abuse condition), treatment will be allowed, and appropriate referrals will be made. Individuals who are currently engaging in short-term (e.g., 12-week protocol) evidence-based treatment will not be eligible until treatment has ended. - Access to internet and home computer or tablet device that will allow telehealth delivery of intervention. - Available to attend either intervention group at the times they are scheduled. - Enrolled and eligible to receive care in Veterans Health Administration (VHA). We will facilitate enrollment for Veterans not currently enrolled but wish to take part in the study. 	
prior experience who do not currently engage in regular practice at this level will be eligible.)
 
 - High risk from a mental health perspective e.g., recent psychiatric hospitalization, high risk flag or a note in their VA electronic health record indicating current high-risk factors, entered into a drug or alcohol detoxification or rehabilitation program, or attempted suicide within the previous year as indicated in their VA electronic health record. - Pregnant or breastfeeding or plans to become pregnant within the year, assessed via self-report. Enrollment of pregnant or breastfeeding participants could potentially complicate outcomes, as new symptoms are likely to arise during the course of the intervention that are attributable to the pregnancy or breastfeeding and not the intervention or symptoms related to PTSD. - Reports difficulty standing on feet for the majority of a Tai Chi class (approximately 60 minutes). - Reports that they have been told by a doctor that they should not engage in physical activity unless recommended by a medical team. - Reports other reason they cannot safely participate in physical activity. - Concurrent participation in another clinical trial - Participants who engage in behavior that is disrespectful or disrupts the group may be terminated from the study. - Participants who demonstrate evidence of falsifying data may be terminated from the study
--	---

4.5 Study Evaluations

Our primary evaluation measures for this feasibility trial will be measures of feasibility, acceptability, and adherence. Our secondary measures will be administered to pilot the administration of psychometric measures for future trials. Evaluations will be conducted during two baseline sessions (prior to randomization), at post-treatment (12-week evaluation), and (for Phase Two only) at 3-month follow-up (24-week evaluation). A VA approved videoconferencing platform (e.g., Cisco Webex, Microsoft Teams) will be used to administer the measures that need to be conducted by staff (see below). Study staff will also instruct participants regarding how to complete the questionnaires collected electronically using the Qualtrics program and will be available to answer participants' questions in order to facilitate completion. Post-treatment and 3-month follow-up assessments will be completed in one or two sessions.

In order for the baseline data to be valid, the baseline assessment should be completed within approximately one month prior to group assignment. The sit to stand task (planned to be administered at the first baseline session) may be readministered closer to the group start date if delays have taken place. Also, if participants were unable to complete the sit to stand task at the first baseline assessment (e.g. if they do not have an appropriate chair available), it may be completed later.

A. Primary Measures: Feasibility and Acceptability, Measures of Participant Satisfaction and Adherence	
Measure	Description, Citation, and Metric for Current Study
The Client Satisfaction Questionnaire (CSQ)	
The CSQ assesses participants satisfaction with patient care³⁹. Administered at post-treatment, and 3-month follow-up (for Phase Two only) via Qualtrics. There are 8 original items that focus on client satisfaction and 3 supplementary items that measure global life satisfaction, general health status and global effectiveness of services received.
 
Metric: At least 70% of participants will have a mean item-score of 3 or greater on the 1-4 scale of the 8 original items at post-treatment.

Participant Adherence Attendance/Compliance	
Study staff will monitor number of missed sessions, reasons given for missing sessions, and completion of assessments.
 
Metric: 75% of participants will attend at least 70% of the treatment sessions. 70% of participants will complete all assessments (baseline through follow-up).

Credibility/Expectancy Questionnaire (CEQ).	
Assesses participants' perceptions of treatment credibility and outcome expectancy in clinical outcome trials.⁴¹
 
Administered at weeks 1,2,4, and 9 via Qualtrics
 
Metric: At least 70% of participants will report a mean item-score of 6 or greater on the 1-9 scale by week 4 for both credibility and expectancy

Weekly Log Sheets	
Participants will keep logs of homework/practice that will be reported via telephone to the project coordinator weekly during the 12-week intervention period. In the Tai Chi condition, they will record the number of minutes per day spent on home practice. In the Wellness condition, they will record weekly goals.
 
Metric: At least 75% of participants will complete at least 70% of weekly log sheets.

B. Secondary Measures Outcome Measures to Be Administered to Ascertain Burden and Calculate Intra-Class Correlation Coefficients	
Administered at baseline, post-treatment (12-weeks), and 3-month follow-up (24-weeks), for Phase Two only (Note that CAPS-5 will only be administered at baseline and post-treatment for Phase Two)	
Construct and Measure	Description and Citation
PTSD severity: Clinician Administered PTSD Scale – 5th Edition (CAPS-5)	The CAPS-5 is a structured diagnostic interview for PTSD administered by study staff. ⁴² The interviews will take place using a VA approved platform (e.g., Cisco Webex or Microsoft Teams). During Phase Two , this diagnostic interview will be video-recorded, with participant permission and administered at baseline and post-treatment. The recordings will be used to ensure reliability of assessor ratings.
Pain: The Brief Pain Inventory – Short Form (BPI)	The BPI is a self-report measure that examines pain intensity and interference with functioning in various life domains. ^{43,44} Administered via Qualtrics. ^{43, 44}
Medical Outcomes Study Self-Reported Measure of Health Status: 36-Item Short Form Survey (SF-36)	The SF-36 is a 36 item self-report questionnaire that assesses self-perception of health status in the following domains: physical functioning, role limitations due to physical and emotional factors, social functioning, bodily pain, general health, vitality, and mental health. ⁴⁵ Administered via Qualtrics.

Physical Functioning: 30 second Sit to Stand Test (30-s STS)	The 30-s STS is an objective measure of lower body strength. ⁴⁶ Administered by study staff over videoconference platform.
---	---

C. Weekly Outcome Measures to Be Administered to Ascertain Burden

Administered weekly using Qualtrics throughout intervention period (both *Phase One* and *Phase Two*)

Construct and Measure	Description and Citation
PTSD: The PTSD Checklist for DSM-5 (PCL-5)	The PCL-5 is a 20-item self-report measure that examines symptoms of DSM-5 posttraumatic stress disorder criteria over the past week. ^{47,48} Administered via Qualtrics.
Pain: The Brief Pain Inventory – Short Form (BPI)	In addition to being administered at the primary assessment points (baseline, post-treatment, 3-month follow-up) as noted above, the BPI will be administered weekly during the intervention period using Qualtrics. ^{43, 44 43,44}

D. Other Descriptive Measures

Demographics	This information will be used to provide a comprehensive description of the sample of Veterans and variables may be used as covariates in sensitivity analyses. Administered at baseline. Administered via Qualtrics.
Life Events Checklist Extended Self Report	The LEC-5 will be used to establish Criterion A for the CAPS-5 interview with study staff. Administered at baseline. Administered via Qualtrics.
Psychoactive and Pain Medication Usage	A list of current, prescribed psychoactive and pain medications will be obtained through VA electronic medical record and verified through participant self-report at baseline and updated at subsequent assessments. For each prescribed medication, staff will ask whether participants have been taking medications as prescribed during the previous period and will document lapses and changes.

E. Other Measures

Telephone Screening Form	Potential participants will be screened over the telephone by study staff to determine if they meet inclusion criteria. Individuals who meet this initial criteria will be scheduled for the baseline assessment where the Informed Consent will be reviewed and signed.
Feedback Interview Form	Semi-structured interview developed to obtain feedback from each participant about their participation in the study. This feedback will be obtained through interviews that will take place at post-treatment (12-weeks) and, in Phase Two, at 3-month follow-up (24-week evaluation). Interviews will take place using a VA approved platform (e.g., Cisco Webex or Microsoft Teams), and with participant permission, will be video recorded and transcribed.
Additional Feedback Questions	Some additional satisfaction items will be administered via Qualtrics to address participants' response to the specific interventions used in this study.

Personal Health Inventory (PHI)	The PHI is a 12-item self-report measure that assesses participants' relationship with 8 areas of health and well-being from the VA Whole Health Circle (model that is used in the Wellness Intervention) including relationships, sleep, exercise, food and drink, personal development, spirituality, surroundings, and power of the mind. ⁴⁹ This scale will be administered using Qualtrics to participants who are in the Wellness Intervention to measure potential growth across these 8 areas of self-care over the course of the study. It will be administered during the intervention at week 2 and week 12 in Phase 1 , and also at the 3-month follow-up (24-weeks) in Phase 2 .
---------------------------------	--

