Posttraumatic stress disorder (PTSD) affects almost one quarter of military Veterans seeking care from Veterans Administration healthcare facilities. PTSD is associated with many health-related issues, especially chronic musculoskeletal pain, and is increasingly considered a systemic disorder, affecting both mind and body. Accessible treatments that address PTSD and chronic pain are urgently needed. Tai Chi is an ancient Chinese exercise that uses an integrated mind-body approach to enhance quality of life. Tai Chi delivered in groups has been shown to improve both mental health and physical health in patients with a variety of chronic conditions. However, no studies to date have examined Tai Chi for PTSD and pain in Veterans. Since the onset of COVID-19, interventions that can be delivered without the need for face-to-face contact are greatly needed. Remote mind-body interventions delivered via videoconferencing platforms can reduce barriers to treatment for Veterans isolated by PTSD-related avoidance, travel related challenges, or public health social distancing restrictions. The proposed study will evaluate the feasibility of remotely delivered Tai Chi for PTSD and pain in Veterans. This trial represents first steps toward a long-term goal of establishing this mind-body treatment to address these maladies for Veterans via a remote videoconferencing platform. In Phase One, the research team will adapt and do a 'dry run' of two existing 12-week, twice per week interventions (Tai Chi and a Wellness control) for delivery via videoconferencing for the study population. In Phase One, the team will recruit 12 participants (6 in each group) and utilize quantitative and qualitative feedback to refine and standardize the interventions. In Phase Two, 36 participants will be randomly assigned over 3 cohorts ($n = 12$ for each cohort, $n = 6$ for each group) to either a Tai Chi or a Wellness group for 12 weeks with a post-treatment and three-month follow up assessment. The feasibility and acceptability of a remotely delivered randomized trial of these two interventions and the assessment protocols will be determined. Feasibility will be quantified using rates of participant eligibility, recruitment, attrition, and adherence to the treatment and assessment protocols. Feasibility will be indicated (1) by the ability to meet recruitment goals, including women and minority participation, and (2) by having at least 75% of participants regularly attend sessions and engage in home practice and 70% complete post-intervention and follow-up assessments. Acceptability will be assessed via participants' ratings on a standardized measure of treatment satisfaction, supplemented by qualitative exit interviews. Acceptability will be indicated by 70% of the participants reporting treatment satisfaction and credibility. Information from this trial will be utilized to design a large, randomized control study evaluating the efficacy of Tai Chi for improving outcomes for Veterans with PTSD and chronic musculoskeletal pain. The proposed study will be pivotal to establish procedures to fully evaluate a novel, accessible, nonpharmacologic approach for symptom management of PTSD and chronic pain in a future large-scale trial of Tai Chi.

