participant via a secure videoconferencing platform approved by VA Boston for patient use (e.g. Cisco Webex, Microsoft Teams). Study details and alternatives to participating in the study will be reviewed. If participants report that they understand the study procedures and are willing to participate in the study, staff will ask participants to sign the ICF and HIPAA forms either electronically using DocuSign program or on a hard copy with a wet signature if unable to do so electronically. (See below for Informed Consent Process).

Dropout/Unenrollment

Participants will not be unenrolled in the study if they do not attend sessions. We will use an intention-to-treat approach and attempt to capture all potential data at all assessments unless participants request that we do not contact them. (Examples: If a participant does not attend the post-treatment assessment, we will nonetheless contact them to ask them to complete the 3-month follow-up. If a participant gets a new job and cannot attend group sessions, we will nonetheless contact them for the post-treatment and follow-up assessments. If a participant tells us that they would like to drop out of the study and do not want to be contacted for additional assessments, we will not contact them again.) A dropout will be defined as someone who requests that we do not contact them again for study assessments.

Use of Email

Study staff may use e-mail with participants to send: 1) instructions on how to access the remotely delivered intervention groups, 2) date, time and link to assessments that will be conducted remotely, and/or 3) previously approved participant manuals or measures to participants as needed (e.g. if postal mail is delayed or participants ask for copies), **3) a standardized email with instructions for the baseline assessment.** Standard VA-approved language indicating that Veterans should not reply to these e-mails will be included in each e-mail.

Risks to Human Subjects

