4.7 Data Analysis

Sample Size Calculation

In this pilot study we are primarily concerned with feasibility and data gathering with a target goal of 48 participants (12 in *Phase One* and 36 in *Phase Two*). Based on our prior experience, we feel confident we can reasonably recruit 48 participants during the study period over 4 waves of recruitment for these intensive (twice per week for 12 weeks) interventions. From our previous experience with remote Tai Chi groups, we found 6 to be an optimal group size as it permitted the instructor to see each participant well on the video screen to provide individualized attention and facilitated a feeling of camaraderie among the participants. For this study's primary outcomes of satisfaction (measured by the CSQ) and credibility of the interventions (measured by the CEQ), we anticipate that more than 70% of the participants will meet the metrics identified. If 26 of 36 participants enrolled in *Phase Two* meet the metric the estimated completion percent would be 72% (95% CI: 55% to 86%). For the primary outcomes of compliance/attendance (measured by sessions and assessments attended), and completion of weekly log sheets, we anticipate that more than 75% of the participants will meet the metrics identified. If 28 of 36 participants enrolled in *Phase Two* meet the metric the estimated completion percent would be 77% (95% CI: 60% to 89%).

Phase Two of this trial will use an individually randomized group treatment trial (IRGT) design, where individual participants are randomized to one of the interventions and the interventions are delivered in small groups. In *Phase Two*, after a cohort of approximately 12 eligible participants are identified, research staff will contact eligible participants by phone to confirm that they still wish to participate in the study and are able to attend sessions at the days and time of the interventions. Once confirmed, half will be randomly assigned to each of the two conditions (Tai Chi and Wellness). If we are unable to recruit 12 Veterans over a one-month recruitment push, we may randomize a smaller cohort of Veterans so that Veterans who have agreed to participate will not be kept waiting too long to begin the interventions.

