- Credibility will be measured by the CEQ with at least 70% of participants reporting a credibility rating of 6 or greater on the 9-point scale.
- Compliance with home practice will be measured by 75% of participants completing 70% of weekly log sheets.

Measures to be examined for participant burden for the larger trial will assess PTSD symptom severity, pain levels, global health, and physical functioning at baseline, post-treatment and (for *Phase Two* only) 3-month follow-up. In the qualitative feedback interviews, we will further assess these issues to determine if changes are needed regarding recruitment, retention, adherence, and participant burden. If we do not meet the feasibility goals, we will reevaluate to make refinements before developing protocols for a future large trial.

AIM 3. We will utilize information from this trial to plan and design a large, randomized control study evaluating the efficacy of Tai Chi compared to Wellness for improving outcomes for Veterans with PTSD and chronic musculoskeletal pain.

The Tai Chi and Wellness control protocols developed, revised, and finalized as part of the proposed project will be used in a future larger study designed to evaluate Tai Chi for PTSD and chronic pain. The current study will provide preliminary data on feasibility, acceptability, adherence, and participant burden. In addition, the preliminary trial will allow us to work out technology issues to optimize our use of remote videoconferencing and to develop methods to maximize efficiency for research staff that will help guide the design of this large-scale trial. If we fall short of recruitment and/or retention goals, we will use the information gathered during the qualitative interviews and study staff experience to make further refinements to our remote protocol (e.g. providing additional resources for assistance with technology issues for participants, providing videocams or tablets to all participants, assistance with home setup, etc.).

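### Does the plan need a written rule for how a missing CSQ or CEQ, or a Veteran terminated by the team, counts toward the Phase Two goals?

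*Combined protocol and SAP*

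**What the plan says.** The abstract defines acceptability in one sentence: "Acceptability will be indicated by 70% of the participants reporting treatment satisfaction and credibility". Section 4.5 turns this into two numerical goals.

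- **CSQ:** "At least 70% of participants will have a mean item-score of 3 or greater on the 1-4 scale", using the eight original items at post-treatment.
- **CEQ:** "Administered at weeks 1,2,4, and 9 via Qualtrics", with the goal "At least 70% of participants will report a mean item-score of 6 or greater on the 1-9 scale by week 4", applied to the credibility and expectancy parts alike. Section 4.7 (Aim 2) restates the credibility part without a week: "at least 70% of participants reporting a credibility rating of 6 or greater on the 9-point scale".

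Section 4.5 also sets a retention goal: "70% of participants will complete all assessments (baseline through follow-up").

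Three places bear on the denominator.

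- Section 4.1, Dropout/Unenrollment, adopts an intention-to-treat approach and says "Participants will not be unenrolled in the study if they do not attend sessions". It defines a dropout only as someone who asks not to be contacted again.
- The sample size text in section 4.7 names the CSQ and CEQ and works an example that begins "If 26 of 36 participants enrolled in" Phase Two, giving 72% (95% CI 55% to 86%).
- The exclusion column of section 4.4 allows termination for disrupting the group or falsifying data, and section 5.0 allows the PIs to discontinue a participant after an SAE. Neither mentions the analysis.

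**The concern.** Attendance, log sheets and assessment completion are counts, so a missing one is simply not met. The CSQ and CEQ are scores, and an absent score can be treated as not met, left out or imputed. The plan does not say which. Nor does it say whether an earlier CEQ can stand in for a missing week 4 form.

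Termination raises a similar question. The two termination bullets sit among the exclusion criteria, although a group can be disrupted only after it has started, which in Phase Two is after randomisation. Read as exclusions, they would take a Veteran out of the denominator. Read with the intention-to-treat text in section 4.1, they would not.

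At stake is the acceptability verdict that Aim 3 carries into the larger trial. A missed goal could reflect unreturned forms rather than dissatisfied Veterans, and a denominator chosen after the data are seen could follow the preferred answer.

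**Working it through.** **Inputs.** 36 randomised (the Phase Two target, sections 4.1 and 4.7); a 70% pass mark for the CSQ and CEQ and 70% for retention (section 4.5). The number returning the post-treatment CSQ is not given in the plan, so a range is shown.

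**The plan's own figure.** 26/36 = 72.2%. The exact (Clopper-Pearson) 95% interval is 54.8% to 85.8%, which matches the stated 72% (55% to 86%). The plan's example therefore uses 36 as its denominator.

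**Pass marks.** The smallest passing count over a denominator d is ceil(0.70 × d). Over all 36 it is ceil(25.2) = 26. The retention goal is likewise met at 26 of 36, since 25/36 = 69.4% falls short. Over n responders it is ceil(0.70 × n). Counts from that number up to 25 pass over responders and fail over all randomised.

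| CSQ responders | Needed, responders only | Needed, all 36 | Counts with opposite verdicts |
|---|---|---|---|
| 26 | 19 (73.1%) | 26 | 19 to 25 |
| 30 | 21 (70.0%) | 26 | 21 to 25 |
| 34 | 24 (70.6%) | 26 | 24 to 25 |
| 36 | 26 (72.2%) | 26 | none |

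**Chance of passing.** Assume that responders answer independently and that each is satisfied with probability p. The chance is P(X ≥ pass mark), with X binomial(n, p).

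| n | p | Responders only | All 36, missing = not met |
|---|---|---|---|
| 26 | 0.80 | 86.9% | 0.3% |
| 26 | 0.85 | 96.8% | 1.5% |
| 26 | 0.90 | 99.7% | 6.5% |
| 30 | 0.80 | 93.9% | 25.5% |
| 30 | 0.85 | 99.0% | 52.4% |
| 30 | 0.90 | >99.9% | 82.5% |
| 34 | 0.80 | 93.8% | 77.3% |
| 34 | 0.85 | 99.1% | 94.1% |
| 34 | 0.90 | >99.9% | 99.5% |

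**How far 26 applies.** The retention goal covers every assessment through the 3-month follow-up, whereas the CSQ goal uses post-treatment only. A Veteran who misses only the follow-up fails retention but still has a CSQ score. So 26 CSQ responders is the lowest number consistent with meeting the retention goal, not the number that goal implies. None of these counts transfers to the CEQ, which is collected during treatment and whose missingness the retention goal does not fix.

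**Termination.** 25/36 = 69.4% fails and 25/35 = 71.4% passes, so removing one Veteran changes the verdict at that count. The plan gives no expected number of terminations.

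**What the text already supports.** Each goal is a percentage of participants who will have or will report a score at the threshold, and a Veteran with no score does neither. With intention-to-treat in section 4.1 and 36 enrolled as the denominator in section 4.7, the plain reading is all randomised, with missing as not met.

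**The case for a change.** The strongest case for a change is that none of the supporting passages is a scoring rule. The intention-to-treat sentence is illustrated by continued contact and data collection, and the 26 of 36 example is a precision calculation in which every status is known. An analyst could report the percentage of respondents satisfied without contradicting any sentence, and at 26 responders that choice moves the chance of passing from under 7% to over 86%. A written rule would need only wording and no new data.

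The silence and the arithmetic stand. Three things weaken the call for a change.

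- **The causes can be separated.** Completion of assessments is a monitored primary measure with its own goal, so unreturned post-treatment forms will be known. Exit interviews supplement the ratings.
- **The obvious rule has a cost.** Making missing = not met decisive causes the satisfaction goal largely to re-measure retention. Section 4.7 also allows up to 20 randomised per cohort, 60 in all over three cohorts, to secure an average of 12 able to take part. If 60 were randomised and 36 responded (an assumption), the goal would need 0.70 × 60 = 42 satisfied, more than the number responding. Which figure should decide is a matter of judgement.
- **Termination from the study is not removal from analysis.** Sections 4.4 and 5.0 allow the former and do not mention the latter. The contrary reading rests on which table column holds the bullets.

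The missing week in the Aim 2 restatement of the CEQ goal is an abbreviation of section 4.5, not a conflict. The narrow dropout definition enters no goal.

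**Conclusion.** The concern does not call for a change. The plan leaves unstated how a missing CSQ or CEQ is scored, which administration satisfies the week 4 wording, and whether a terminated Veteran stays in the denominator. Its own text leans to all randomised with missing as not met, and no stated rule is shown to give a wrong result.

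The choice can reverse the satisfaction verdict for 19 to 25 satisfied Veterans if only 26 of 36 return the form, for 24 to 25 if 34 do, and for none if all do. The counts assume 36 randomised; the pass probabilities also assume independent answers and satisfaction of 0.80 to 0.90 among responders.

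The consequence of a reversal is limited. Section 4.7 says that unmet goals lead the team to re-evaluate and refine before the larger trial, and sets no stop rule. Analysts would ordinarily fill the gap by giving the all-randomised figure with the responder percentage and the number of responders beside it, from data the plan already collects.
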